3.5.2 Biomarker analysis

Biomarkers will be taken at study time points in accordance with the protocol.

The exploratory biomarker data will not be included in the CSR, and the analysis is not described in this SAP.

3.5.3 Pharmacogenetics research (PGx)

Data collected in the pharmacogenetics research will not be included in the CSR, and the analysis is not described in this SAP.

3.5.4 Pharmacodynamics research (PD)

Data collected in the pharmacodynamics research will not be included in the CSR, and the analysis is not described in this SAP.

3.5.5 Sputum Induction

Data collected in the sputum induction research will not be included in the CSR, and the analysis is not described in this SAP.

4. ANALYSIS METHODS

4.1 General principles

The analysis of the study outcome variables will include all data captured during the 52-week double blind treatment and follow-up period. This includes data regardless of whether IP was prematurely discontinued or delayed, and/or irrespective of protocol adherence, unless the patient withdraws consent or assent to study participation.

A summary table which counts patients who have been incorrectly randomised and who received incorrect treatment will be presented.

Summary data will be presented in tabular format by treatment. Categorical data will be summarized by the number and percentage of patients in each category. Continuous variables for parametric data will be summarized by descriptive statistics including N, mean, (standard deviation) SD, median, and range.

Minimum and maximum values will be reported to the same degree of precision as the raw data unless otherwise stated. Mean, median, SD, confidence intervals (CIs), geometric mean and CV will be reported to one further degree of precision. Percentage frequencies will be presented to one decimal place.

Given the number of endpoints in the secondary analyses, multiplicity procedures will not be used to attempt to control 'alpha' across all secondary endpoints.

All data will be listed. Data listings will be sorted by treatment and subject number. Summaries by visit will include baseline but not visits intended for screening and randomisation.

All hypothesis testing will be reported using 2-sided tests except for the primary analysis which will be 1-sided and the p-value will be presented to 4 decimal places. Where confidence

intervals (CI) are presented for treatment comparisons these will be presented as 2-sided 95% CIs.

Plots of data by visit or visit window will cover the entire study period including follow-up.

4.2 Analysis methods

4.2.1 Patient disposition, demography data and patients characteristics

Patient disposition will be summarized using the All Patient analysis set.

The number of enrolled patients will be summarized. The number and percentage of patients within each treatment group will be presented by the following categories; randomised, not randomised (and reason), received study treatment, did not receive study treatment (and reason), completed treatment, discontinued treatment (and reason), completed study, and discontinued study (including reason).

The number and percentage of patients, who discontinued IP, but remained in the study will be presented by treatment group. Kaplan-Meier plots will be produced summarizing the time (in days) to discontinuation of IP and withdrawal from the study.

Demographic data such as age, gender, race and ethnicity will be summarized by treatment group for the FAS.

Various baseline characteristics will also be summarized by treatment for the FAS. These include weight, height, body mass index (BMI), medical, surgical and respiratory disease histories, history of allergic rhinitis, FEV₁ (pre and post-BD) at baseline, age at onset of asthma, asthma duration, the number of asthma exacerbations in the previous 12 months, the number of asthma exacerbations requiring hospitalizations in the previous 12 months, number of exacerbations resulting in antibiotic treatment, type of recent exacerbations, the number of admissions to ICU (Intensive Care Unit) for asthma during the hospitalization, eosinophil count, smoking status, nicotine consumption, reversibility test.

The following covariates are deemed to be of interest for inclusion in the statistical models of the primary and secondary endpoints. Possible covariates include but are not limited to: age at first asthma allergy status, whether hospitalized within the last year, race, sex, baseline spirometry variable measurements, baseline PEF, baseline ACQ-5 and baseline asthma symptom scores. For Blinded Deliverable review analyses, the following five covariates have been selected: age, race, sex, age at first asthma allergy status and whether hospitalized within the last year. For the final analysis, only age and gender will be included as covariates in the statistical models.

Medical and surgical histories will be summarized by using the latest version of MedDRA Preferred Term (PT) within the System Organ Class (SOC) level of MedDRA. For medical history, conditions are identified as current or past in the eCRF HISM page. Surgical history is specified in the HISS eCRF page.

4.2.2 Prior and Concomitant Medications

The number and percentage of patients who had prior medications and take concomitant medications will be presented by treatment group for the FAS. Concomitant medications will be classified according to the AstraZeneca Drug Dictionary. The summary tables will present medications by generic term using Anatomical Therapeutic Chemical (ATC) classification system codes.

Separate tables will be presented for all medications received during the following periods

- Prior: Medications with a start and stop date before Visit 2 date (first day of IP). If the stop date is missing or partial and it cannot be determined whether the subject stopped the drug before the start of study medication, the medication will be considered as concomitant.
- Concomitant medications while on treatment: Medications with start date \leq the last day of IP and stop date \geq the first day of IP. If the start or stop date is missing or partial and cannot be determined, the medication will be considered as concomitant. If the medication started whilst on IP and was ongoing (no stop date) then this is also a concomitant medication.
- Concomitant medications during follow-up: Medications categorised as ‘Concomitant’ that are still ongoing one day after the last day of IP, and also
 - Medications with start date $>$ last day of IP and \leq date of Visit 21; this is only applicable for subjects that are treated for the entire treatment period
 - Medications with start date $>$ last day of IP and \leq the last day of IP + 1 week; this is only applicable for subjects that prematurely discontinue IP

Previous disease-related treatments will also be tabulated.

Tables for maintenance medications (started prior to and ongoing after the first day of IP) will be produced displaying the baseline total daily dose of ICS and LABA. The number of patients using other maintenance asthma medications at baseline will also be summarised. In addition, the total number of days of oral glucocorticosteroid treatment associated with asthma exacerbations per patient from the first day of IP up to Week 52 will also be summarised.

Medications will be classified according to the AstraZeneca Drug Dictionary (AZDD). Percentages will be calculated relative to the number of patients in the FAS.

Data from patients who discontinued IP, where possible and relevant, be included in the appropriate medication summaries.

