4.2.2 Dose Adaptation Procedure

Given the well-known potential for flu-like symptoms from TLR9 agonism, dosing for each patient will be adapted based on the individual's flu-like AEs. The flu-like symptoms usually respond well to paracetamol (and otherwise resolve spontaneously within 24-48 hours following dosing), and the dose adaptation should be based on the assessment of flu-like symptoms after intake of paracetamol.

After the first 4 doses an assessment of the individual patient will be performed according to experiences of flu-like AEs (arthralgia, chills, pyrexia, myalgia) within 24h of inhalation, with adaptation of AZD1419 accordingly:

If no or only mild flu-like AEs occur after the first 4 doses, then the subsequent doses will be stepped up to 8 mg.

If any severe flu-like AEs occur after any of the first 4 doses, then the subsequent doses will be stepped down to 1 mg.

Otherwise, the subsequent doses will be maintained at 4 mg.

All patients will continue dosing with placebo or AZD1419 at the adjusted levels until they have received a total of 13 inhaled weekly doses.

[figure not shown]
All dosing decisions are subject to investigator judgment. If an investigator believes that a patient is not tolerating a dose for any reason, the next dose can be reduced independent of the rules described above.

Dosing will be stopped in patients who do not tolerate a 1mg dose and they will be followed for an additional 4 weeks for safety before they discontinue the study.

Since e.g. side effects from influenza vaccination could potentially impact the interpretation of the flu-like symptoms after the dosing of study drug, it is suggested that such vaccination should be performed e.g. 2 days after a dose of IMP.

For definition of severity of AE (including flu-like symptoms), see Section 6.3.3.

Figure 2 Dosing

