4.3 Follow-up period/Observation period

After the treatment period patients are followed until they experience loss of asthma control or for the whole period of up to 52 weeks (Visit 21). For details of the study assessments during the observation period refer to the Schedule of events, Table 1.

Patients will be monitored with regards to safety, tolerability and efficacy aspects during the whole study period. In addition to assessments performed at the clinical visits, an ePRO device coupled with a home spirometer will on a daily basis capture asthma symptoms, reliever use and lung function (PEF) and a FeNO meter measurements will be performed every second day.

At any time during the tapering period or after, when patients experience loss of asthma control as defined below, they will resume their usual ICS+LABA asthma controller therapy and will be considered to have reached the primary endpoint. They will then stop IMP administration and will be followed for an additional 4 weeks in the study.

For the purpose of the study Loss of asthma control is defined as any of the following:

- a) An increase of ACQ-5 to 1.5 or more
- b) A reduction of 30% or more in morning peak expiratory flow (PEF) from baseline on 2 consecutive days
- c) At least six additional reliever inhalations of SABA in a 24-hour period relative to baseline on 2 consecutive days
- d) An exacerbation requiring systemic corticosteroids

Upon a), b) or c) being fulfilled, an automatic asthma action plan will be triggered in the ePRO device prompting the patient to resume their usual ICS + LABA medication. In addition an alert will be sent to the site/Investigator. Upon receiving such an alert the Investigator should contact the patient and arrange a visit to the clinic for evaluation, see Section 5.1.3.1. Blood sampling for biomarkers should be part of this evaluation.

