8.5.1 Patient disposition, demography data and patients characteristics

Patient disposition will be summarized using the All patients analysis set.

The number of enrolled patients will be summarized. The number and percentage of patients within each treatment group will be presented by the following categories; randomized, not randomized (and reason), received study treatment, did not receive study treatment (and reason), completed treatment, discontinued treatment (and reason), completed study, and discontinued study (including reason).

Demographic data such as age, gender, and race will be summarized by treatment group for the full analysis set.

Baseline characteristics will also be summarized by treatment for the full analysis set. These include medical, surgical and respiratory disease histories, weight, height and BMI, smoking status, history of allergy, FEV₁ (pre and post-BD) at baseline, asthma duration, age at onset of asthma, asthma medications, the number of asthma exacerbations in the previous 12 months, and the number of asthma exacerbations requiring hospitalizations in the previous 12 months.

Medical and surgical histories will be summarized by MedDRA Preferred Term (PT) within the System Organ Class (SOC) level of MedDRA.

The number and percentage of patients who take concomitant medications, and those who take disallowed concomitant medications during the study, will be presented by treatment group. Concomitant medications will be classified according to the AstraZeneca Drug Dictionary. The summary tables will present data by generic term using Anatomical Therapeutic Chemical (ATC) classification system codes.

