4.2.3.1 Exposure

Extent of exposure to IP is defined as the number of days between the start and the end dates of study therapy:

$$\text{Extent of exposure (days)} = (\text{Last dosing date} + 7 \text{ days}) - \text{first dosing date} + 1.$$

Dosing period of IP is up to and including week 12, i.e. there is a maximum of 13 weekly doses. The calculation for study treatment exposure is consistent across all patients including those who prematurely discontinued. Expected dosing administrations can be determined by number of weeks from first dose to discontinuation.

Extent of therapy summaries will be provided for the safety and FAS analysis sets. The numbers and percentages of subjects falling into each category will be presented for each treatment group, presenting N, mean, SD, median and range.

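### For patients who stop IP early, the follow-up medication table closes one week after the last dose, although stops for loss of control or intolerance are followed for four more weeks

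*SAP*

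**What the plan says.** SAP 4.2.2 defines separate medication tables for prior, on-treatment and follow-up periods. The follow-up table has three routes of entry:

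- Concomitant medication "that are still ongoing one day after the last day of IP, and also" is carried over.
- New starts after the last day of IP count up to Visit 21, but "this is only applicable for subjects that are treated for the entire treatment period".
- For everyone else, new starts count up to "the last day of IP + 1 week; this is only applicable for subjects that prematurely discontinue IP".

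The SAP gives no reason for the shorter limit.

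The protocol follows early stoppers for longer. On loss of control, section 4.3 says "They will then stop IMP administration and will be followed for an additional 4 weeks in the study". For patients who do not tolerate the lowest dose, section 4.2.2 says "they will be followed for an additional 4 weeks for safety before they discontinue the study".

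Protocol 8.5.1 asks for the number and percentage of patients by arm who take concomitant medication. It adds that "those who take disallowed concomitant medications during the study, will be presented by treatment group". SAP 4.2.2 has no table of disallowed medication.

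**The concern.** Loss of control during the dosing period ends IMP. The patient then becomes an early stopper in the SAP's terms and gets the 7-day window, while the protocol continues observation for 4 weeks. A drug first started after day 7 is not on-treatment medication, is not carried over and is not a new start within the window. It is collected and listed but enters no period table. A patient who received all doses and started the same drug after the same interval would be counted.

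The SAP is also uneven with itself. Section 3.4.1 counts adverse events up to Visit 21, and section 3.3.4 keeps exacerbations that occur after IP has stopped. An event in week 3 after the last dose can thus be tabulated while a drug started to treat it is not. In a withdrawal trial, readers will use these tables to see which treatments patients needed after control was lost.

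**Working it through.** **Length of the gap.** Inputs: a window of 7 days (SAP 4.2.2), follow-up of 4 weeks = 28 days (Protocol 4.3), and weekly dosing to week 12 (SAP 4.2.3.1: "Dosing period of IP is up to and including week 12, i.e. there is a maximum of 13 weekly doses"). If control is lost *u* days after the last dose, with *u* between 0 and 7 and no further dose given, follow-up ends 28 + *u* days after that dose.

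- Shortest: 28 days followed, 7/28 = 25% covered, 21 days uncovered.
- Longest: 35 days followed, 7/35 = 20% covered, 28 days uncovered.

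The protocol fixes no follow-up length for other early stops, so these are not sized.

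**Does the controller restart fall in the gap?** Under criteria a to c of the loss-of-control definition, "an automatic asthma action plan will be triggered in the ePRO device prompting the patient to resume their usual ICS + LABA medication". Take loss of control as uniform over the 7 days after the last dose, with a restart *d* days later. The share of restarts beyond day 7 is *d*/7:

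- same-day restart: 0%
- 1 day: 1/7 = 14%
- 3 days: 3/7 = 43%

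The delays are assumptions. With a prompt restart, most are counted.

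**How many patients get the short window through loss of control?** The plan states no such figure. Its sample-size section (Protocol 8.2) gives 20% and 60% controlled at week 52, and those rates reproduce its event count. The hazard ratio is ln 0.60 / ln 0.20 = 0.317. Events by Schoenfeld's formula at two-sided 0.05 and 90% power are 4(1.960 + 1.282)² / (ln 0.317)² = 31.9, so 32 as stated.

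Under a constant hazard from the week 6 taper, loss by week 12 is:

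- placebo: 1 − 0.20^(6/46) = 18.9%, or 6.6 of 35
- active: 1 − 0.60^(6/46) = 6.4%, or 2.3 of 35

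Under a constant hazard from week 0, replacing 6/46 by 12/52, the figures are 31.0% and 11.1%, or 10.9 and 3.9 of 35. With 81 randomised (40.5 per arm, SAP 1.3), the ranges are 7.7 to 12.6 on placebo and 2.6 to 4.5 on active.

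These are patients to whom the rule applies. They are not patients with a medication omitted. That would need the rate of new starts after day 7, which the documents do not give.

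**Disallowed medication.** The SAP amendment history (6 September 2018) records that this table was deleted from 4.2.2, so the removal was deliberate. SAP section 1 says changes from the protocol will be described in section 6. Section 6 does not list this one.

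**The case against.** The strongest reply is that little of importance is lost, and most of it stands.

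- Controller restart is prompted at the event and normally falls within one dosing interval.
- SABA is allowed throughout. An ongoing record enters by carry-over, and SAP 4.2.4.4 summarises diary reliever use by week and arm.
- SAP 4.2.2 itself summarises oral steroid days for exacerbations from first IP to week 52. Only non-oral or unrelated courses escape.
- The tables count patients by drug, so a drug begun inside the window counts whatever its duration.
- All data are listed (SAP 4.1). SAP 4.2.2 also closes with a general intention to include IP discontinuers in the medication summaries where it makes sense. That sentence does not override the explicit one-week limit.
- Disallowed use remains an important deviation under SAP 2.2, tabulated after physician review, though only for the randomised treatment period.

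Three stronger readings are tempting, and the documents support none of them.

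- A reader might infer that the rule hides more medication on placebo. Loss of control alone points that way, at about 3 to 1 under the design rates. But IMP also stops for intolerance and adverse events, plausibly more often on active, and no rates are given.
- A reader might infer that the drug's benefit is understated. The table is descriptive. Loss of control and severe exacerbations come from the EXACA module and moderate exacerbations from MED1, and none of them uses these windows.
- A reader might infer that patients who complete dosing and lose control later have no valid end date because they never reach Visit 21. Visit 21 is only an upper limit, and it does not bind for someone who leaves sooner.

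**Conclusion.** The mismatch is real and limited. For early stops due to loss of control, the SAP's window covers 20% to 25% of the time followed after the last dose. Medication first started in the remaining 3 to 4 weeks is in no period table. This follows from the wording alone, given weekly dosing and no dose after the event. The same one-week limit meets a 4-week follow-up after intolerance.

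What drops out is mainly later treatment: antibiotics, non-oral systemic steroids, and added or late-restarted controllers. How often that happens cannot be derived from the documents, and the difference between arms has no established size or direction. The primary and secondary efficacy analyses are unaffected. On disallowed medication, the remaining fault is that a protocol table was removed without appearing in the SAP's list of changes.

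**What to change.** In SAP 4.2.2, replace the two end dates with one rule for all patients: start date after the last day of IP and on or before the patient's last study date (EOT/ED or Visit 21). If one week is intended for early stoppers, state why.

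Either restore the by-arm disallowed-medication table in Protocol 8.5.1 or list its removal in SAP section 6.

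Separate rows for ICS, LABA and systemic corticosteroids started before and after loss of control would help interpretation but are optional.

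The cost is SAP wording and minor table reprogramming. Medication dates are already collected.

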4.2.3 Exposure and Compliance

Extent of exposure to IP by compliance, total treatment duration by mean daily dose, and recordings on eDiary will be summarized by treatment group and using both the safety analysis set and full analysis set.

The date and time of all IP administrations, and all missed doses will be listed using the safety analysis set.

4.2.3.1 Exposure

Extent of exposure to IP is defined as the number of days between the start and the end dates of study therapy:

$$\text{Extent of exposure (days)} = (\text{Last dosing date} + 7 \text{ days}) - \text{first dosing date} + 1.$$

Dosing period of IP is up to and including week 12, i.e. there is a maximum of 13 weekly doses. The calculation for study treatment exposure is consistent across all patients including those who prematurely discontinued. Expected dosing administrations can be determined by number of weeks from first dose to discontinuation.

Extent of therapy summaries will be provided for the safety and FAS analysis sets. The numbers and percentages of subjects falling into each category will be presented for each treatment group, presenting N, mean, SD, median and range.

4.2.3.2 Compliance

Compliance will be summarized for each treatment group, presenting mean, standard deviation, 1st quartile, median, 3rd quartile, and range. In addition, the following compliance categories will be derived: <80%, 80% -120%, >120%. The numbers and percentages of subjects falling into each category will be presented for each treatment group. Missing responses will not be imputed. Data collected prior to Visit 2 (Week 0) will not be included in the compliance calculations.

In addition, the total number of dosing administrations will be calculated per patient. The maximum number of possible dosing administrations for IP is 13. If the patient withdraws from the study before the 12 week dosing period is completed, the total number of dosing administrations expected depends on the duration of the patient in the study. Compliance is defined as:

$$\text{Compliance (\%)} = (\text{Number of dosing administrations made/number of dosing administrations expected}) \times 100$$

Compliance for PEF

The PEF will be monitored morning and evening. Patients will perform 3 successive peak flow manoeuvres while sitting or standing, capturing the highest value for morning and

evening manoeuvres. Protocol states that Investigator will check patient's adherence to correct use of the hand-held spirometer at each visit.

$$\text{Compliance (\%)} = (\text{Number of recordings made / number PEF recordings expected}) \times 100$$

If a patient completes the 52 weeks of the study, they would be expected to have a maximum of 2 recordings per day for 365 days i.e. 730 recordings. If the patient withdraws from the study early, the total number PEF recordings expected is based on the duration of the patient in the study.

Compliance for FeNO

Although FeNO is measured by patients using the NIOX Vero device once in the morning every second day as well as at the clinic at designated visits, compliance will be calculated using the recordings from the NIOX Vero device at home only.

$$\text{Compliance (\%)} = (\text{Number of recordings made / number FeNO recording expected}) \times 100$$

If a patient completes the 52 weeks of the study, they would be expected to have a maximum of 1 recording every other day for 365 days i.e. 183 recordings. If the patient withdraws from the study early, the total number FeNO home recordings expected is based on the duration of the patient in the study.

Compliance for eDiary

The ePRO device is used by the patients to record various measurements twice a day, morning and evening as well as night-time awakenings once every day.

$$\text{Compliance (\%)} = (\text{Number of recordings made / number recordings expected}) \times 100$$

If a patient completes the 52 weeks of the study, they would be expected to have a maximum of 2 recordings per day for 365 days i.e. 730 recordings. If the patient withdraws from the study early, the total number eDiary recordings expected is based on the duration of the patient in the study.

Compliance for ACQ-5

ACQ-5 will be self-administered within the ePRO once weekly during the study. Compliance is based on the Overall ACQ-5 Score.

$$\text{Compliance (\%)} = (\text{Number of Overall ACQ-5 scores recorded / number of Overall ACQ-5 scores expected}) \times 100$$

If a patient completes the 52 weeks of the study, they would be expected to have a maximum of 52 ACQ-5 scores. If the patient withdraws from the study early, the total number ACQ-5 scores expected is based on the duration of the patient in the study.

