4.2 Treatment period

When patients are comfortable using the prescribed inhalers and have gone through the inclusion/screening assessments the patients may be randomized. An ACQ-5 score of ≤ 0.75 is required for randomization. A total of 70 patients are planned to receive 13 weekly doses of IMP (1:1) during the conduct of the study. Study drug will be administered as a nebulized inhalation (using the I-neb® device (Philips Respironics)) at the clinic. The patients will be observed at the clinic for at least 6 hours after the first dose and for at least 2 hours after the remainder of doses.

Patients will receive placebo or AZD1419 at 4 mg/week for 4 weeks, after which each patient's dose will be maintained or adjusted up or down based on the individual patient's frequency and severity of flu-like AEs (defined in [Section 6.1.1](#)) appearing within 24 hours after dosing, see [Figure 2](#). All decisions are subject to investigator judgment. If an investigator believes that a patient is not tolerating a dose for any reason, the next dose can be reduced independent of the rules described. Further instructions on Dose Adaptation are included in [Section 4.2.2](#).

During the dosing period, patients will have ICS + LABA controller medications tapered down and discontinued. LABA will be stopped on the evening prior to receiving dose 7 (Visit 8), and ICS will then be gradually tapered down and discontinued during the next 3 weeks. The first week after LABA discontinuation, the patients will receive their usual full dose of ICS. The week thereafter the total daily ICS dose will be reduced by 50% and the week thereafter the total daily dose will be reduced to 25% of the patient's usual full dose of ICS. ICS is discontinued in the evening prior to receiving IMP dose 10 (Visit 11). The regimen for tapering down the ICS according to the above guidelines will be decided by the Investigator for the individual patient, i.e. as appropriate the Investigator will adjust the ICS dose down and

potentially change dosing regimen from BID to QD to achieve half and then a quarter of the daily dose of ICS. Patients will be able to use SABA reliever therapy as needed at all times during the study. Reliever use will be monitored on a daily basis in the ePRO device, as a component of asthma control throughout the trial.

For details of all assessments done during the treatment period refer to Section 5 and for timing of the procedures refer to Table 1.

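### Read literally, SAP 4.2.3.2 counts doses after a protocol-mandated stop as expected, so patients who took every permitted dose but stopped before dose 11 are classed as under 80% compliant; SAP 4.2.3.1 gives a conflicting rule

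*SAP*

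**What the plan says.** SAP 4.2.3.2 defines IP compliance as doses given divided by doses expected, times 100. On the denominator it says "The maximum number of possible dosing administrations for IP is 13" and, for a patient who withdraws before the 12-week dosing period is complete, "the total number of dosing administrations expected depends on the duration of the patient in the study". Results are sorted into three bands: below 80%, 80% to 120%, and above 120%.

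SAP 4.2.3.1, on exposure, gives another rule for the same quantity: "Expected dosing administrations can be determined by number of weeks from first dose to discontinuation". It does not say whether IP or study discontinuation is meant.

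Protocol 4.3 sets out what follows loss of control. It applies as follows: "At any time during the tapering period or after, when patients experience loss of asthma control as defined below". The patient resumes controller therapy, and then: "They will then stop IMP administration and will be followed for an additional 4 weeks in the study". Protocol 4.2.2 contains a second stop of the same shape: "Dosing will be stopped in patients who do not tolerate a 1mg dose and they will be followed for an additional 4 weeks". Neither SAP section mentions either stop.

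**The concern.** In this withdrawal design the primary event can occur inside the dosing period. Protocol 4.2 stops LABA the evening before dose 7 and ICS the evening before dose 10. If time in the study sets the denominator, up to four weekly doses after a mandated stop count as expected and not given. A fully adherent patient is then reported as poorly compliant, and the lowest band mixes non-adherence with the primary event and with intolerance.

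The two SAP sections can also give different percentages for the same patient, and a programmer has no guidance on which to follow. SAP 4.2.3 asks for a listing of all missed doses; without a settled definition of an expected dose, it is unclear whether a dose after a mandated stop belongs there.

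**Working it through.** **Inputs.** Weekly dosing, Week 0 to Week 12, at most 13 doses (SAP 4.2.3.1 and 4.2.3.2), so dose k is given at Week k-1. IMP stops at loss of control from the start of tapering, with 4 further weeks in the study (Protocol 4.3). Proportion still controlled at Week 52: 20% placebo, 60% active (Protocol 8.2, SAP 1.3). Allocation 1:1 (Protocol 3.5). 81 patients randomised (SAP 1.3).

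**Check on the planning rates.** Hazard ratio = ln 0.6 / ln 0.2 = 0.317. Schoenfeld events = 4 × (1.960 + 1.282)² / (ln 0.317)² = 31.9, rounded up to 32. This matches the plan's 32 events. The point does not rest on it, but it shows how the 20% and 60% were used.

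**Compliance of a patient who misses no permitted dose.** The patient takes k doses, loses control before dose k+1 and leaves 4 weeks later. By time in the study, the expected number is min(13, k+4). Two alternatives are shown: 13 for everyone (if leaving after the 4-week follow-up is not treated as withdrawal), and one post-stop dose fewer, min(13, k+3). If expected doses end when IP stops, the result is k/k.

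| Last dose k | k / min(13, k+4) | k / 13 | k / min(13, k+3) | k / k |
|---|---|---|---|---|
| 6 | 60.0% | 46.2% | 66.7% | 100% |
| 7 | 63.6% | 53.8% | 70.0% | 100% |
| 8 | 66.7% | 61.5% | 72.7% | 100% |
| 9 | 69.2% | 69.2% | 75.0% | 100% |
| 10 | 76.9% | 76.9% | 76.9% | 100% |
| 11 | 84.6% | 84.6% | 84.6% | 100% |
| 12 | 92.3% | 92.3% | 92.3% | 100% |
| 13 | 100% | 100% | 100% | 100% |

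The row k = 6 needs loss of control between the LABA stop and dose 7. The group below 80% is the same under the first three rules: stops before dose 11, that is, before the Week 10 dose. The 1 mg intolerance stop follows the same formula. For example, a stop after dose 5 gives 5/9 = 56%.

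**Share of each arm affected by the loss-of-control route (assumption: constant hazards).**
- Hazard from randomisation: λ = -ln(S)/52, which is 0.0310 per week on placebo and 0.0098 on active. P(event in Weeks 6 to 10) = exp(-6λ) - exp(-10λ) = 9.7% and 3.6%.
- Hazard starting at Week 6: λ = -ln(S)/46. P = 1 - exp(-4λ) = 13.1% and 4.3%.
- With 81/2 = 40.5 patients per arm, this is about 3.9 to 5.3 placebo and 1.5 to 1.8 active patients.
- If instead 10% to 50% of each arm's Week 52 events fall in that window (assumption), the shares are 0.8 × (10% to 50%) = 8% to 40% on placebo and 0.4 × (10% to 50%) = 4% to 20% on active.
- With no treatment effect, this route creates no difference between arms.

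**The case against.** The best defence is that SAP 4.2.3.2 does not have to be read this way. Its sentence on duration is conditional on withdrawing before the dosing period is complete. A patient who loses control at Week 8 or later is still in the study at Week 12, so the condition is not met. The only text that speaks to patients who stop dosing early is then SAP 4.2.3.1. That section is about IP exposure, so IP discontinuation is a natural reading, and it gives 100%.

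This stands as far as it shows a conflict rather than one settled wrong rule. It does not remove the problem. Where the condition is not met, the only number that 4.2.3.2 offers is 13, and the classification below 80% is unchanged. SAP 4.2.1 separately counts patients who stopped IP but stayed in the study, and plots the two times separately. The SAP therefore treats these as different events, and 4.2.3.2 names the study one.

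A second objection is that a reader can already see why dosing stopped. SAP 4.2.1 tabulates treatment discontinuation with reason by arm, and SAP 4.2.3 lists all administrations. This largely stands: a reader might infer that non-adherence and mandated stopping cannot be told apart, and the documents do not support that. Two gaps remain. The tabulated reasons do not correct the percentage, and the list in Protocol 3.9 has no entry for loss of control, so these stops may be recorded as other.

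**Conclusion.** The point holds as a conflict between two adjacent SAP rules. The literal reading of 4.2.3.2 gives a wrong compliance figure for patients who took every permitted dose and stopped before dose 11. The size in each arm rests on the planned control rates and an assumed hazard shape.

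Three stronger readings are tempting, and the documents do not support them:
- **Every fully adherent patient who loses control is misclassified.** Stops after dose 11 or 12 score 85% or 92% and stay in the middle band.
- **The table will show poorer adherence on placebo.** That needs the assumed treatment effect. The 1 mg intolerance stop creates the same artefact and could fall more on active, since Protocol 4.2.2 links flu-like symptoms to TLR9 agonism. The net direction is open.
- **The efficacy results are affected.** Compliance defines no analysis set and enters no model or test. The full analysis set is defined irrespective of protocol adherence (SAP 2.1.2), and the log-rank test is untouched.

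The effect is confined to descriptive compliance reporting. It should be corrected because the reported figure would be wrong and the correction is simple.

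**What to change.** Use one definition in SAP 4.2.3.1 and 4.2.3.2. Expected doses are the weekly doses scheduled from dose 1 to the earliest of dose 13, any protocol-mandated stop of IP (loss of control, intolerance of the 1 mg dose, pregnancy) and study withdrawal. State how other IP discontinuations, such as those for adverse events or by patient decision, are counted. Apply the same definition to the listing of missed doses. A correction for loss of control alone would leave the artefact in place for the other mandated stops.

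In the existing table of treatment discontinuation by arm (SAP 4.2.1), show loss of control as its own reason.

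With this definition, every patient in the table under working scores 100%. The cost is a change of SAP wording and one derivation line, with no new data.
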